#### 1.- Introduction/Justification

Motor imagination (MI) is defined as the cognitive process of imagining the movement of a part of a person's own body without actually moving that part of the body (Al-Saegh et al.,2021).

IM training in healthy adults has been shown to improve strength, arm positioning speed, and joint range (Dickstein and Deutsch, 2007). On the other hand, the capacity of MI has been shown to be related to proprioception. Shenton et al (2004) have suggested that proprioception, in some circumstances, may represent an important input at the sensory level that contributes to the representation of the body; Furthermore, McCormick et al (2007) have suggested that altered proprioceptive input could alter MI tasks.

The research question of this work is based on seeing if the relationship between IM and the aforementioned parameters also occurs the other way around. Could improving strength and/or manual dexterity also improve IM?

Neuromuscular electrical stimulation (NMES) is an application of electrical stimulation used in movement rehabilitation Stein et al

(1992). Functional electrical stimulation ( *FES*) is a subtype of NMES in which stimulation supports functional and purposeful movements Popovic et al (2001). This technique consists of applying electrical currents to the muscles, making them contract in a sequence that allows you to perform different tasks. Some of the examples are: holding a key, holding a toothbrush, standing or walking Vodovnik et al (1978).

The technology was developed in the 1960s, during which initial clinical use began, emphasizing its potential as an assistive device Hoshimiya et al (1989). Since then, FES has evolved into an important therapeutic intervention that rehabilitators can use to help people with diseases or injuries to the nervous system regain their ability to stand, walk, reach and grasp Buckett et al (1988) , having demonstrated positive effects in

increased muscle strength, remission of osteopenia and improved walking (Bélanger et al, 2000; Sabut, 2011).

FES device technology has traditionally been based on conventional electrodes. However, multi-field surface electrodes have emerged, consisting of groups of several small conductive fields, which can be activated/deactivated and configured independently (FesiaGrasp, 2022).

The Fesia Grasp system is a FES-based neurological hand rehabilitation device developed by Fesia Technology (Donostia-San Sebastián, Spain). This is a commercial device designed for manual dexterity rehabilitation, which delivers a train of biphasic pulses of different widths and amplitudes to different electrode fields asynchronously, meaning that different electrode fields are activated with an interval predefined between pulses Malešević et al (2017).

Fesia Grasp, generates superficial electrical stimulation of the forearm muscles to trigger eight different flexion and extension movements of the wrist and fingers in order to restore the function, freedom and independence of the patient's hand after a stroke, Martin -Odriozola et al (2021).

The study aims to answer the PICO research question:

Q: healthy adults

I: FES and, multfield FES.

C: video games

O: Motor imagination, strength, manual dexterity.

The aim is to compare different tools in a population sector to check if there is an improvement in motor skills through the use of FES.

2.- Objectives

General objective:
 
 
• Check the effects of FES and virtual reality regarding motor imagination, strength and manual dexterity.
 
 
Secondary objectives:
 
 
• Find out if functional electrical stimulation improves motor imagination, both kinesthetic and visual, as well as manual dexterity and strength.
 
• Find out if an intervention based on the use of virtual reality improves motor imagination, both kinesthetic and visual, as well as manual dexterity.
 
• Check if there are differences between FES, multi-field FES, and virtual reality in terms of visual motor imagination, kinesthetic and manual dexterity.
 

3.- Project description

The present work is a clinical, randomized study of parallel groups of a quasi-experimental type.
 
A sample of university students will be divided into 4 groups, where one of them will act as a control group (without intervention), and the other three will perform hand training with two different types of FES devices (conventional and multi-field). and a last group will receive hands-on training with video games.
 
Intergroup analyzes will be performed before the start of training (pre-intervention), after finishing the program (post-intervention), and three weeks after finishing (follow-up evaluation). Likewise, intragroup analyzes will be carried out to check whether the training has caused an improvement in the quality of motor imagination, as well as an improvement in manual dexterity in each of the groups.
 
To carry out the project, a collaboration agreement will be signed with the company FESIA TECHNOLOGY SL, which will provide a FESIA GRASP device for the study, as well as the consumables (electrodes) necessary for the development of the study. The agreement is currently being evaluated by the UBU legal office.
 
It is planned to register the study on the international platform Clinicaltrials.gov.

4.- Material and methods

4.1 Type of study
 
Controlled, randomized, parallel group clinical trial. Unicentric, and with blind evaluation by third parties. Quasi-experimental.
 
4.2. Description of devices
 
Four parallel groups are planned. A first group that will have an intervention based on multi-field FES with the FESIA GRASP device; another group that will receive only FES

with the Globus Elite electrostimulation device (device with conventional electrodes); a third group that will receive an intervention based on virtual reality; and finally a control group, which will not receive any treatment.

The three devices are described below.

#### 4.2.1. Description of the FESIA GRASP

The Fesia Grasp device bases its operation on superficial electrical stimulation of the antebrachial muscles to provoke flexion and extension movements of the wrist, thumb, index and fingers 3, 4 and 5. The device has the CE marking.

The main feature of this device is its multi-field electrode, which allows a greater number of movements to be selected, doing so quickly and selectively, and it is also possible to combine the movements with each other. The device is composed of a stimulator, a multi-field electrode, a textile band and a software application. The stimulator generates electrical pulses, which are transmitted to the skin through the multi-field electrode. It is a matrix electrode designed to cover a large part of the surface of the forearm and thus be able to stimulate the muscles of the neuromuscular groups of the radial, ulnar and median nerves. It is composed of 32 cathodes (output fields) and 8 anodes (return fields), which can be activated independently or combined, allowing it to be adapted to the anthropometry of different patients. The multi-field electrode is personal and disposable, with an estimated life of two weeks of daily use.

The textile band ensures correct contact of the electrode with the skin and, on the other hand, serves as a support for both the stimulator and the electrode. The device allows the generation of 8 different isolated movements (flexion and extension of the wrist, thumb, index and fingers 3, 4 and 5).

Furthermore, it is possible to combine these movements with each other, with the aim of creating functional movements such as: clamp, lateral clamp, palmar grip, etc.

Finally, Fesia Grasp has a software application on a tablet that allows, on the one hand, to control and configure the stimulation parameters and, on the other, to monitor the evolution of the different patients/users in an easy and intuitive way. The application is FesiaPro, and is designed to be used by healthcare personnel.

#### 4.2.2. Description of the Globus Elite 4-Channel Electrostimulator The

Globus Elite 4-Channel Electrostimulator is a traditional electrical stimulation device, which allows up to 8 electrodes to be activated at the same time (4 channels). The device, which has a CE marking, allows the use of different types of electrical currents, which are selected based on the desired therapeutic objectives and the evolutionary phase of the person.

Among the currents that can be applied are the currents that the Fesia Grasp device also emits. These are currents with a biphasic and symmetrical rectangular pulse shape, low frequencies, constant pulse widths and high intensities.

#### 4.2.3. Description of the VirtualRehab video game for hand

VirtualRehab is a therapeutic physical rehabilitation tool that uses reality

virtual to provide therapy to patients with neurological or musculoskeletal disorders; providing a wide range of activities designed to improve mobility, coordination and strength. This tool is based on the idea of gamification in rehabilitation, where patients participate in virtual games that require physical movements to complete challenges. These games adapt to the needs and abilities of each patient, allowing personalized rehabilitation.

VirtualRehab allows: a) a comprehensive evaluation; b) personalized treatment planning; c) monitoring and tracking patient progress. This tool has different fine motor games, specifically it includes 8 video games for fine motor training that can be customized for the needs of each patient.

#### **4.3 Sample**

The sample will be composed mainly, although not exclusively, of adults of legal age, belonging to the group of university students.

##### 4.3.1. Type of sampling and access to the sample

Participation in the study will be proposed to students of the Faculty of Health Sciences of the University of Burgos, so it is a convenience sampling.

The sample will be randomized through a computer application for assignment within one of the groups contemplated in the study.

##### 4.3.2. Inclusion and exclusion criteria

The following inclusion criteria are established:

- a) Be of legal age and sign the informed consent.
- b) Not suffer from any pathology in the upper limb such as tendinitis, edema, fractures, etc.
- c) Intact skin (no breaks, scratches, cuts, and other types of superficial or deep injuries) on the arm where the devices will be placed if applicable.

As exclusion criteria:

- a) Severe medical problems.
- b) Use a pacemaker.
- c) Being pregnant.
- d) Peripheral neuropathies.
- e) Presence of other neuromuscular pathologies

Participants may leave the study in the following cases:

- a) At your own request, without giving reasons.
- b) Adverse events occur that prevent the study from continuing.
- c) Non-compliance with treatment. Failure to complete sessions on schedule for each one.

The reason for abandonment will be recorded in the database.

A sample of between 20-25 subjects per group is expected.

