#### **4.6. Description of the intervention.**

As explained, the study will consist of 4 groups.

Each group will receive a total of 5 sessions (Figure 1). Next, it is explained what each of the 4 groups will do.

4.6.1 Control group: This group will not receive any type of intervention and will continue with their usual routine. A commitment will be requested that they do not begin any physical activity other than that previously carried out for the duration of the study.

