#### 4.6.2 FESIA GRASP Group:

There will be 5 30-minute sessions, and the 2 available protocols will be used: training and grip.

Protocol 1: Training: It will be

used during the first half of the first session so that the participant becomes accustomed to the sensation of electrical stimulation through an automatic sweep of electrical stimulation.

Protocol 2: Grip

It will be used in sessions 1-5, both inclusive. Firstly, the device configuration will be carried out, selecting the combinations of cathodes that generate clearer flexion and extension movements of the wrist, thumb, index and fingers 3, 4 and 5. If the motor threshold is not found in any user for any of the movements, or it is considered that it may be harmful or not beneficial to stimulate any of these, it will not be selected. It will be important to do this setup thoroughly in the first session, and minor variations will be made in subsequent sessions.

Next, the therapy will begin. This will progress as follows (it will be adjusted depending on the patients' progress):

- Sessions 1-3: selective contractions of the forearm muscle groups.
- Weeks 4-5: training in activities of daily living with the help of FES

The general development proposed during sessions 1-3 is as follows:

- Startup (5 minutes): Place the device and verify that the previous configuration is correct.

- First part (5 minutes): selective contractions of the different groups muscles through FES.
- Second part (10-15 minutes): voluntary selective contractions by the

patient, guided by the therapist.

The general development proposed during sessions 4-5 is as follows:

- Startup (5 minutes): placing the device and verifying that the previous configuration is correct.
- First part (5 minutes): selective contractions of the different groups muscles through FES.
- Second part (10-15 minutes): inclusion of functional movements previously activated in functional actions through FES: grasping objects of different sizes.

The selected electro-parameters will be those preconfigured by default in the systems from Fesia, both in the training protocol and in the grip protocol: 25 Hz frequency, 250 us pulse width. The intensity will be 5 mA above the motor threshold, the motor threshold being the minimum intensity at which the movement of the limb is perceived visually. If the patient cannot tolerate such intensity, he will limit himself to the maximum intensity at which this sensation is pleasant.

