#### 4.6.3. Globus Elite Electrostimulator Group:

You will also carry out 5 sessions of 30 minutes duration. The device will be applied in the following way (it will be adjusted depending on the patients' progress):

- Sessions 1-3: general repetitive contractions of the muscle groups of the forearm.
- Weeks 4-5: training in activities of daily living with the help of FES

The general development proposed during sessions 1-3 is as follows:

- Startup (5 minutes): Place the device and verify that the configuration is correct.
- First part (5 minutes): general contractions of the different groups muscles through FES.
- Second part (10-15 minutes): general voluntary contractions by the patient, guided by the therapist.

The general development proposed during sessions 4-5 is as follows:

- Startup (5 minutes): Place the device and verify that the • configuration is correct.

- First part (5 minutes): general contractions of the different groups muscles through FES.
- Second part (10-15 minutes): inclusion of functional movements previously activated in functional actions through FES: grasping objects of different sizes.

The electro-parameters selected will be the same as those used in the previous group.

Therapy times will vary depending on the patient's fatigue measured using a Borg scale. The score for this should not exceed 3 points out of 10 ( $\leq 3/10$ ), 1 minute after the end of the exercise. If the perception of fatigue is greater, first the intensity (eg frequency of movements) and then the duration of the therapy will be adjusted.

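### Missing scheduled sessions is a ground for leaving the study that only the three active arms can meet, so comparisons with control are open to selection bias

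*Combined protocol and SAP*

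**What the plan says.** Section 4.3.2 introduces its list with "Participants may leave the study in the following cases". Item a) is the participant's own request, item b) is adverse events, and item c) is "Non-compliance with treatment. Failure to complete sessions on schedule for each one". The only provision for people who leave is that "The reason for abandonment will be recorded in the database".

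The sessions belong to the active arms. For multi-field FES (4.6.2), "There will be 5 30-minute sessions". For conventional FES (4.6.3), "You will also carry out 5 sessions of 30 minutes duration". Section 4.6.4 gives the video-game arm the same number and length.

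For control, section 4.6.1 says "This group will not receive any type of intervention and will continue with their usual routine". Its one conduct requirement is "A commitment will be requested that they do not begin any physical activity other than that previously carried out", and no withdrawal is tied to that. The opening of section 4.6 nevertheless says "Each group will receive a total of 5 sessions (Figure 1"), which conflicts with the control description.

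Section 4.4.1 has participants allocated as they are recruited, so sessions follow randomisation. Section 10 plans within-group and between-group analyses but defines no analysis set and no handling of missing data.

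**The concern.** Randomisation makes the four groups comparable at allocation. A rule that lets people out afterwards for poor attendance, and that can operate in only three of the groups, can undo that comparability. An active arm would be filtered on attendance and the control arm would not.

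The outcomes make this plausible. Maximal grip, timed peg and block tests and self-rated imagery (section 4.5) all depend partly on effort and motivation, and so does turning up on five days in one week. If the less motivated leave the active arms, those arms can look better than control without any training effect.

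The first two secondary objectives in section 2 ask whether FES and virtual reality improve the outcomes. The no-intervention arm is what would separate such an effect from practice or retesting, so this is the comparison at risk. Losing participants also costs precision, and section 4.3.2 expects only 20 to 25 per group with no stated allowance for dropout.

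**Working it through.** **The plan's own figure.** The 20–25 per group cannot be reproduced, because no alpha, power, effect size, SD or dropout rate is given. Two-sided alpha of 0.05 and 80% power are assumed below.

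**Who can meet each criterion.**

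| Criterion in 4.3.2 | Three active arms | Control |
|---|---|---|
| a) own request | yes | yes |
| b) adverse events | yes | not excluded by the text |
| c) sessions not completed on schedule | yes, five sessions each | no intervention to miss |

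Only c) is structurally one-sided.

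**Loss and bias in one consistent model.** Assumed inputs are 95% attendance per session, five sessions, removal after a single miss, and a correlation r of 0.3–0.5 between a stable attendance trait T and the outcome. T is standard normal. Each session is attended when √ρ·T + √(1−ρ)·e exceeds −1.645, where e is independent standard normal noise and ρ is the within-person correlation of attendance.

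- Completion = E[Φ((1.645 + √ρ·T)/√(1−ρ))⁵].
- Shift = mean of T among completers, in SD.
- Bias against a complete control arm, with no true effect = r × shift.

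| ρ | Completion | Shift (SD) | Bias, r = 0.3 | Bias, r = 0.5 |
|---|---|---|---|---|
| 0 | 0.95⁵ = 77% | 0 | 0 | 0 |
| about 0.5 (peak) | 83% | 0.245 | 0.07 | 0.12 |
| 0.99 | 94% | 0.13 | 0.04 | 0.07 |

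Loss therefore runs from 6% to 23%, and bias from 0 to about 0.12 SD. The largest loss goes with zero bias: when misses are independent, who completes is chance.

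The result depends on the attendance rate. In the same formula, the peak bias is about 0.04–0.06 SD at 98% attendance and 0.12–0.20 SD at 90%.

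**A simpler check.** Bias = d × g, where d is the share withdrawn and g is the outcome gap in SD between compliers and non-compliers (assumed 0.25–0.75). Type I error is for a two-sided z-test of n(1−d) against n, with n = 20 or 25.

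| d | Bias (SD) | Type I error (nominal 0.05) |
|---|---|---|
| 10% | 0.025–0.075 | 0.051–0.058 |
| 20% | 0.05–0.15 | 0.053–0.079 |
| 30% | 0.075–0.225 | 0.055–0.112 |

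**Precision.** At 77% completion, 20 × 0.774 = 15.5 and 25 × 0.774 = 19.4, taken as 15 and 19. By the noncentral t, the detectable difference against control is:

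- 0.91 SD for 20 v 20, worsening to 0.99 SD for 20 v 15.
- 0.81 SD for 25 v 25, worsening to 0.87 SD for 25 v 19.

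These are worst cases for precision. They occur where the bias is nil, so the full precision loss and the full bias do not arise together.

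**The case against.** The strongest reply is that the text is permissive. It says participants may leave. No sentence says that someone who misses a session is removed, loses later evaluations or has data discarded. The number of missed sessions that triggers c) is undefined, and nothing says whether a make-up session counts. The text also reads as a translation. All of this stands, so a reader should not infer that the active arms will contain only people with perfect attendance. Equally, the plan does not say who decides, or whether a participant who misses one session is evaluated and analysed. That leaves removal to discretion after allocation.

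A reader might also infer that control keeps everyone, or that the comparison is biased as a matter of fact. Neither follows. Control participants can leave under a), and b) is not restricted to active arms. An untreated group asked back for repeat evaluations may lose people too, so the net direction is not certain. If attendance is complete, or unrelated to outcome, criterion c) causes no selection bias.

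The sentence giving every group five sessions does not rebut the point, because section 4.6.1 gives control no session content.

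Finally, five short sessions in one week among volunteer students may produce little loss. At 10% withdrawn the illustrated effect is small beside a detectable difference of 0.8–0.9 SD. The third secondary objective in section 2, which compares the active approaches with each other, is outside this asymmetry. Both arguments limit the importance of the point but do not remove it.

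**Conclusion.** The point holds as a risk to comparisons with control. Criterion c) permits a post-randomisation exit from the study that depends on attendance and can arise only in the active arms, and nothing in the plan offsets it.

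The direction is probably in favour of training, on the assumption that attenders are more motivated. At 95% attendance per session, removal after one miss and r of 0.3–0.5, the bias is at most about 0.12 SD, and it could be nil. None of these inputs comes from the documents.

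A reader might combine the 23% loss with selection wholly determined by motivation, and so reach a bias of 0.12–0.19 SD. That mixes two incompatible models: a 23% loss at 95% attendance requires independent misses, which produce no selection.

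The change should be made because it is cheap and because outcomes not collected cannot be recovered later. Confidence is moderate.

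**What to change.** - Reword c) in section 4.3.2 so that non-compliance is recorded but does not by itself end study participation. The right to withdraw on request under a) is unaffected.
- Invite every randomised participant who has not withdrawn consent to the POST and follow-up evaluations already in the section 4.4.2 timetable.
- In section 10, make analysis by allocated group primary, state how missing outcomes will be handled, and keep a completers-only analysis as a sensitivity analysis.
- Reconcile the section 4.6 sentence on sessions for every group with the control description in 4.6.1.

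The cost is protocol wording and a few more evaluation appointments. The estimated effect may be slightly smaller, because people who did not attend every session are included. The content of the sessions and the safety rules do not change.

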#### **4.4 Process**

There are three phases of the project: Preparation, Data Collection, and a final Analysis and Report Preparation.

